Around 750,000 laparoscopic cholecystectomies are performed in the U.S. every year. This minimally invasive approach has demonstrated to have several advantages like shorter hospital stay, less operative pain and prompt recovery when compared to the open approach (1,2,3,4,5).

Since its first description, the main concern on laparoscopic cholecystectomy has been bile duct injuries, with an estimated incidence rate of between 0.4 and 1 % (6,7,8,9,10). Most common situations involved in a bile duct injury are lack of visualization and tactile feedback, misidentification of structures and anatomic variations (11,12).

Anatomic anomalies have been identified in 19% of patients (13, 14) and hepatic accessory ducts in 8.4% (15,16,17). Different approaches have been proposed to avoid a bile duct injury. Strassberg described the critical view approach of safety dissecting the Calot's triangle and identifying the cystic artery and extra-hepatic biliary ducts (18,19,20,21,22). Even though the critical view approach of safety proved to be very useful, it could not diminish the rate of bile duct injury (23). Pablo Mirizzi (1931) developed the intraoperative cholangiography (IOC), an invasive method to map the intrahepatic and extra-hepatic bile ducts (24,25,26,27,28,29,30). Although the goal was to diminish the severity of the injuries, there are still disadvantages of this technique including:

- radiation exposure for patient and OR staff,
- risk of bile duct injury – during insertion of the trans-cystic catheter,
- the need of bulky material, and
- increased misidentification of the cystic duct.

Recently, a novel technique to visualize structures using fluorescent light and intravenous dye has been developed.

Near Infrared Incisionless Fluorescent Cholangiography (NIFC) is a medical imaging technique that uses fluorescence to detect properly labeled structures during surgery.

NIFC is performed using imaging devices with the purpose of providing real-time simultaneous information from color reflectance images (white light) and fluorescence emission (near infrared light). One or more light sources are used

Multi-center Study Protocol: Efficacy of Near Infrared Incisionless Fluorescent Cholangiography (NIFC) during Laparoscopic Cholecystectomy

to excite and illuminate the sample. Light is collected using optical filters that match the emission spectrum of the fluorophore. Imaging lenses and digital cameras are used to produce the final image.

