Cost effectiveness of the technique was validated by Dip et al (35) with a total of 43 patients (21 males and 22 females). Mean age was 49.53 ± 14.35 years old and mean body mass index was 28.35 ± 8 kg/m² (2). Overall mean operative time was 64.95 ± 17.43 min. NIFC was faster than IOC (0.71 ± 0.26 vs. 7.15 ± 3.76 min; $p < 0.0001$). NIFC was successfully performed in 43 of 43 cases (100%) and intraoperative cholangiography (IOC) in 40 of 43 cases (93.02%) while in 3 patients IOC was not possible. NIFC was less expensive than IOC (US\$14.10 \pm 4.31 vs. US\$778.43 \pm 0.40; $p < 0.0001$). All surgeons found routine use of NIFC useful. Identification rates of extra-hepatic bile duct using NIFC ranges between 71 and 100 % depending on the study (32,33,34,35).

Osayi et al (36) studied eighty-two patients that underwent elective laparoscopic cholecystectomy and compared the use and utility of near infrared

Multi-center Study Protocol: Efficacy of Near Infrared Incisionless Fluorescent Cholangiography (NIFC) during Laparoscopic Cholecystectomy

incisionless fluorescent cholangiography (NIFC) vs intraoperative cholangiography (IOC). Mean age and body mass index (BMI) of the patients were 42.6 ± 13.7 years and 31.5 ± 8.2 kg/m², respectively. Indocyanine green was administered 73.8 ± 26.4 min prior to incision. NIFC was significantly faster to complete than IOC (1.9 ± 1.7 vs. 11.8 ± 5.3 min, $p < 0.001$). IOC was unobtainable in 20 (24.4 %) patients while NIFC did not visualize biliary structures in four (4.9 %) patients. After complete dissection, the rates of visualization of the cystic duct, common bile duct, and common hepatic duct using NIFC were 95.1, 76.8, and 69.5 %, respectively, compared to 72.0, 75.6, and 74.3 % for IOC. In 20 patients where IOC could not be obtained, NIFC successfully identified biliary structures in 80 % of the cases. (39)

Spinoglio et al (40) reported 45 cases between July 2011 and January 2012 with NIFC. The rates of visualization were 93 % for the cystic duct, 88 % for the common hepatic duct, and 91 % for the common bile duct prior to Calot's dissection; after Calot's dissection, the rates were 97 % for all three ducts. Mean hospital stay was 1.1 days and there were no bile duct injuries or any other major complications. (40)

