The studies described above are observational and so far no randomized clinical trial has been published evaluating the efficacy of NIFC to improve the identification of the extra-hepatic biliary structures. Additionally it would be relevant to investigate the ability of the NIFC to reduce intraoperative bleeding, duration of laparoscopic cholecystectomy. Further, it is central to assess whether NIFC can improve the outcomes in some subpopulation of patients for whom the evaluation and dissection of the Calot's triangle is difficult, e.g. obese patients or patients undergoing inflammatory processes. Finally, the potential use of NIFC as a training tool in laparoscopic surgery is still to be studied.

c. Strengths and Limitations

The strength of the study is the ability to investigate whether the extra-hepatic biliary tract is more visible using NIFC when compared with white light (WLI) alone. It is a multicenter study with diverse patient populations and surgeons from different countries/continents that will validate this method globally.

Limitations may include impossibility to randomize by surgeon.

3. Study Overview

The Study is designed to compare the effectiveness of Near Infrared Fluorescence Cholangiography (NIFC) to standard white light imaging (WLI) in visualizing and identifying the main biliary and hepatic structures (Cystic Duct, Right Hepatic Duct, Common Hepatic Duct, Common Bile Duct, Cystic-CBD junction, Cystic-Gallbladder junction and any Accessory Ducts) during laparoscopic cholecystectomy.

4. Study Objectives

a. Primary Objective:

Multi-center Study Protocol: Efficacy of Near Infrared Incisionless Fluorescent Cholangiography (NIFC) during Laparoscopic Cholecystectomy

Demonstrate that NIFC performs better than standard white light (WLI) alone in visualizing and identifying extra-hepatobiliary structures (Cystic Duct, Right Hepatic Duct, Common Hepatic Duct, Common Bile Duct, Cystic-CBD junction, Cystic-Gallbladder junction, and any Accessory Ducts) before and after dissection during Laparoscopic Cholecystectomy (LC).

b. Secondary Objectives:

1. Demonstrate that NIFC is an effective teaching tool to assist students and residents present in the O.R. during the procedure to identify extra-hepatobiliary structures (before/after dissection).
2. Demonstrate that the Time to Clip, which is defined as the time from the moment Calot's Triangle is first visualized to when the clip is applied, is reduced when using NIFC vs WLI alone.

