- Incidence of Anatomic Anomalies of the extra-hepatic biliary system, including any Accessory Ducts
- Incidence of performing IOC
- Incidence of CBD stones
- Incidence of Conversion to open surgery
- Incidence of Bile Duct Injury (BDI)?

iv. For NIFC arm only

- PRIOR to and AFTER DISSECTION: Surgeon/Observer documents which extra-hepatic biliary structures are identified without doubt using the "Reflux Maneuver" during NIFC
- Was the "reflux maneuver" useful?
- Surgeon preference: Was NIFC helpful?

c. One-week Post-Op data collection (usual control after surgery)

- Length of hospital stay

- Readmission?
- Complications?
 - Adverse drug reactions
 - Hemorrhage
 - Bile leak
 - Bile duct injury
- Death?

10. Subject Selection

a. Inclusion Criteria

1. Patients of both genders
2. Minimum age: 18 years old
3. Spoken and written command of the language spoken in the country's center
4. Ability to understand and follow the study procedures and sign the informed consent

b. Exclusion Criteria

1. Known allergies to iodides
2. Known history of cholangitis, pancreatitis, CBDS's, coagulopathy
3. Known liver disease
4. Women who are pregnant or breastfeeding, or for whom possibility of pregnancy was not ruled out

11. Study Device

a. Indocyanine Green (ICG) Fluorescent Dye

The drug used in these studies to evaluate the extra-hepatic bile duct is indocyanine green (ICG) and the equipment uses a wavelength around 800 nm (32,33,34,35,36,37). ICG, a cyanine dye, has been used in various medical diagnostic procedures since its FDA approval in 1956 (38).

ICG is a fluorophore responding to near-infrared irradiation that absorbs light between 790 and 805 nm, and re-emits it with an excitation wavelength of 835 nm. When given intravenously, ICG binds to plasma proteins and becomes confined to the intravascular space [15]. It is then exclusively metabolized by the liver and excreted by the biliary system 15 to 20 minutes after administration. These properties, in conjunction with the absence of any native biological fluorescence within these wavelengths, make ICG an ideal agent for the acquisition of high-quality images of the biliary tract.

b. Equipment

KARL STORZ (Tuttlingen, Germany) has developed a laparoscopic fluorescence imaging system that is suitable for both near-infrared fluorescence and xenon

Multi-center Study Protocol: Efficacy of Near Infrared Incisionless Fluorescent Cholangiography (NIFC) during Laparoscopic Cholecystectomy

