c. Patient Randomization

Each surgeon will follow the standard laparoscopic surgical protocol of his/her center, and will comply with the following additional steps according to which arm of the study the patient is assigned:

i. Control arm (WLI only) procedures

1. After inserting the scope in the abdominal cavity, once other standard operatory procedures (e.g., taking down adhesions if necessary, or releasing scar tissue) are completed using white light imaging (WLI) only, the Researcher will record the time when Calot's triangle is first visualized. From this moment on, the surgery will be recorded.
2. After removing the fat from the gallbladder area, lifting the gallbladder over the liver, and grabbing the Hartman's pouch to visualize the Calot's triangle, but PRIOR TO DISSECTION, the Researcher will determine what extra-hepatic biliary structures can be specifically identified. Of note: because one of the goals of the Study is to evaluate NIFC as a teaching tool, residents and juniors should record what structures they were able to identify by themselves before any intervention of the attendant surgeon.
3. Then, AFTER DISSECTION, a similar assessment of what extra-hepatic biliary structures can be specifically identified using WLI only will be performed.
4. Anatomic anomalies of the biliary system will be documented on the case form and if an anatomic variation is found, a snap shot photo will be taken in addition to the video.
5. Immediately before clipping or proceeding with open surgery, the total time from Step 1 will be recorded, known herein as the "Time to Clip";

6. Before leaving the operation room, all participant surgeons and observers will complete the Intra-Operative Case Report Form (Appendices D and E, respectively).

ii. Experimental arm (NIFC) procedures

1. Patient randomized to the experimental arm, at least 45 mins before surgery, will receive a weight-scaled dose of indocyanine green (0.05 mg/kg) by IV and the time of administration and any adverse reactions will be recorded.
2. After inserting the scope in the abdominal cavity, once other standard operatory procedures (e.g., taking down adhesions if necessary, or releasing scar tissue) are completed using white light imaging (WLI) only, the Researcher will record the time when the Calot's triangle is first visualized. From this moment on, the surgery will be recorded.

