3. AFTER-DISSECTION

A. Document visualization of extra-hepatic biliary anatomy:

For both arms, scope the Calot's triangle area using STD (white-light) mode. If in the NIFC arm, toggle between STD and ICG modes on light source as needed. Check the appropriate boxes below based on what is visible:

	Yes	Maybe	No
Cystic Duct			
Right Hepatic Duct			
Common Hepatic Duct			
Common Bile Duct (CBD)			
Cystic-CBD junction			
Cystic-Gallbladder junction			
Accessory Ducts			

B. For NIFC Arm Only: "Reflux Maneuver" Attempted? Yes No

Repeat the Reflux Maneuver. Check the appropriate boxes based on what is visible:

	Yes	Maybe	No
Cystic Duct			
Cystic-CBD junction			
Cystic-Gallbladder junction			

4. Time to Clip: Time the Cystic Duct was clipped: _____ AM / PM

5. Volume of Bleeding: _____ mL in the bucket/bag or from anesthesia chart at the conclusion of the procedure

6. Bile Leakage: No Yes If yes, Liver bed Other: _____ Did NIFC help identify leak? Yes No

7. Anatomic Anomalies: No Yes If yes, describe: _____

If yes, do you feel NIFC helped you identify this anomaly? Yes No N/A (WLI arm)

8. Was IOC performed? Yes No

9. Were CBD Stones present? Yes No Not Checked

10. Was the procedure converted to Open? Yes No

If yes, explain why: _____

11. Was there a Bile Duct Injury (BDI) during the surgery? Yes No

If yes, complete the BDI Form as described in the Study Protocol.

12. SURGEON FEEDBACK after NIFC:

Did you feel NIFC made your procedure SAFER? Yes No

Were you more CONFIDENT using NIFC vs WLI alone? Yes No

Would you PREFER to use NIFC again vs WLI alone? Yes No

e. Intra-Op Case Report Form – Observer

Near Infrared Incisionless Fluorescent Cholangiography (NIFC)

INTRA-OPERATIVE CASE REPORT FORM - OBSERVER

INSTITUTION: _____

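### Time to Clip includes any X-ray cholangiography done before the timed clip, and the planned data cannot separate avoided cholangiography from faster identification

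*Combined protocol and SAP*

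**What the plan says.** Section 4.b, item 2, aims to show that "the time from the moment Calot's Triangle is first visualized to when the clip is applied, is reduced when using NIFC vs WLI alone". Section 12.c makes this an elapsed time in both arms: "Immediately before clipping or proceeding with open surgery, the total time from Step 1 will be recorded". Nothing is deducted. Item 4 of the surgeon form (Appendix D) takes a single clock reading, "Time the Cystic Duct was clipped".

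IOC is foreseen in both arms. Section 9.b.iii lists "Incidence of performing IOC" among the items collected after dissection, and item 8 of the surgeon form is a Yes/No box with no times. The protocol has no rule of its own on when IOC is done; under section 12.c, "Each surgeon will follow the standard laparoscopic surgical protocol of his/her center". Section 2.a names a risk of bile duct injury "during insertion of the trans-cystic catheter", so the procedure enters the same duct whose clipping is timed.

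Section 2.b cites two durations: "NIFC was faster than IOC (0.71 ± 0.26 vs. 7.15 ± 3.76 min" and "NIFC was significantly faster to complete than IOC (1.9 ± 1.7 vs. 11.8 ± 5.3 min".

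Section 13.b compares time to clipping between arms with an unadjusted Kruskal-Wallis test. IOC is not among the covariates in section 6. Section 8.d says that surgeons cannot be blinded and that allocation is 1:1 within site.

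**The concern.** Objective 2 is framed against white light alone, but a WLI case that includes IOC has had a second imaging procedure. If that procedure falls between first view of Calot's triangle and the recorded clip, its minutes count as Time to Clip. A surgeon without fluorescence may feel more need for IOC than one who has it, and knows the arm when deciding. A shorter NIFC time could then repeat what the rationale already reports, that NIFC is quicker than IOC, and say little about identification under fluorescence compared with white light.

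A Yes/No field cannot repair this afterwards. IOC use is decided after randomisation, so adjusting for it or dropping IOC cases could bias the comparison.

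**Working it through.** **The plan's own figures.** The protocol gives no effect size, standard deviation or power for Time to Clip, so there is no stated figure to reproduce. The IOC and NIFC durations are cited results, taken as they stand.

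**Inputs from the documents.** 500 patients per arm (13.a). IOC takes 7.15 ± 3.76 or 11.8 ± 5.3 min, and NIFC 0.71 ± 0.26 or 1.9 ± 1.7 min (2.b). The test is Kruskal-Wallis (13.b). The clock starts at first view of Calot's triangle (4.b).

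**Assumptions.** Time to Clip without IOC is lognormal, at 20 ± 10, 30 ± 10, 30 ± 15 or 30 ± 17.43 min; 17.43 is the SD of whole operative time in one cited study. NIFC does not change identification speed. All IOC falls inside the interval. The test is at two-sided 5%, so the nominal rate of declaring NIFC faster is 2.5%. IOC shares by arm are illustrative.

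**Step 1: mean shift if NIFC viewing adds no time.** Spurious gain = (IOC share in WLI − IOC share in NIFC) × IOC minutes.
- 30% vs 10%: 0.20 × 7.15 = 1.43 min; 0.20 × 11.8 = 2.36 min
- 20% vs 10%: 0.10 × 7.15 = 0.72 min; 0.10 × 11.8 = 1.18 min
- 15% vs 10%: 0.05 × 7.15 = 0.36 min; 0.05 × 11.8 = 0.59 min

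**Step 2: mean shift if viewing time is added to every NIFC patient.** The sentences that give IOC time also give NIFC time, and toggling between modes happens inside the same interval. Taking the cited viewing time as wholly extra to the white-light look, subtract 0.71 or 1.9 min.
- 30% vs 10%: 1.43 − 0.71 = 0.72 min; 2.36 − 1.9 = 0.46 min
- 20% vs 10%: 0.715 − 0.71 = about 0; 1.18 − 1.9 = −0.72 min
- 15% vs 10%: 0.36 − 0.71 = −0.35 min; 0.59 − 1.9 = −1.31 min

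A negative value means that NIFC looks slower.

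**Step 3: simulated rank-test results** (1,000 to 2,000 trials per setting; ranges run over the assumed time distributions and both IOC durations).

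| IOC use, WLI vs NIFC | NIFC declared faster, no viewing time | NIFC declared faster, viewing time added | NIFC declared slower, viewing time added |
|---|---|---|---|
| 30% vs 10% | about 36–92% | about 6–21% | 0–2% |
| 20% vs 10% | about 11–40% | 0–2% | 2–31% |
| 15% vs 10% | about 6–13% | 0–1% | 7–65% |

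**Step 4: null cases.** With no viewing time added, equal IOC use (30% in each arm) or IOC wholly after the recorded clip gives two-sided rejection in about 5–6% of trials, which is nominal. Removing IOC minutes from each patient's time in the 30% vs 10%, 11.8-minute case gives 5.1–5.6%.

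**The case against.** The other side has five points.

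- **Centre practice does not bias the comparison.** Allocation is 1:1 within site, so a centre's IOC policy balances across arms. This stands. Only arm-dependent choices by unblinded surgeons can create the imbalance; no section says they will occur, and no IOC rate is given. Excluding patients with known duct stones, cholangitis or pancreatitis may also keep IOC use low.
- **Nothing places IOC before the timed clip.** Section 9.b.iii and the surgeon form both list the clip time ahead of IOC. List order is not chronology, but the point stands as a condition on the concern.
- **NIFC viewing takes time too.** This stands and greatly changes the size: at the smaller gaps the bias vanishes or turns against NIFC.
- **Avoided IOC may be a real benefit of assignment.** Section 2.b asks whether NIFC shortens the operation, and elapsed time answers that. Net time also gives the WLI arm the anatomical information from IOC at no cost in minutes. This stands, and is why net time should not replace the endpoint.
- **The data are partly there.** IOC incidence is collected by arm, and surgery is recorded from first view of Calot's triangle, so durations might be recoverable. But no such extraction is planned, and incidence alone shows an imbalance without saying how many minutes it explains.

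A reader might infer the stronger claim that NIFC will look faster only because more WLI patients have IOC. The documents do not support that: they establish neither an imbalance nor the order of IOC and clip.

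**Conclusion.** The concern holds as one of interpretation, and is conditional. Time to Clip mixes identification time with any IOC that precedes the timed clip, and the planned fields cannot separate them. Bias towards NIFC needs two things that the documents leave open: more IOC in the WLI arm, and IOC before the recorded clip.

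If both hold at 30% against 10% use, the chance of declaring NIFC faster with no gain in identification speed runs from about 6–21% (cited viewing time added to every NIFC patient) to about 36–92% (none added), against a nominal 2.5%. The shares and the spread of Time to Clip are assumptions. The upper range should not be read as the expected error rate, nor the result as false if the question is the elapsed time of an NIFC strategy. What the plan cannot support as written is the further conclusion that identification itself is faster than under white light.

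**What to change.** - Add IOC start and end times to item 8 of the surgeon form, and state in item 4 which clip is timed, identically in both arms. IOC use stays with the centres.
- Keep elapsed Time to Clip as the defined secondary endpoint.
- Prespecify in section 13.b a supplementary analysis of Time to Clip minus any IOC minutes inside the interval, and report it beside the elapsed time and IOC use by arm.
- Limit the conclusion on objective 2 to the elapsed time of the NIFC strategy unless the supplementary analysis agrees.
- In the same edit, reconcile the start of the clock: first view in section 4.b, start of hilar dissection as baseline in 9.b.ii, and Step 1 in 12.c, which in the NIFC arm is the dye injection.

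The cost is two time fields, one clarified form item and one extra analysis, with slightly more recording in IOC cases. Net time remains supplementary because IOC is a post-randomisation event.
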